The earliest intervention study (55), conducted in Nottingham, England, consisted of an educational program to encourage early symptom reporting in over 13,000 men and women over age 40 registered with three general medical practices. Patients were instructed to telephone a special hospital number for chest pain lasting more than 10 minutes. Patients from three intervention practices reported chest pain earlier than patients in 10 comparison practices. There was a lower percentage of definite and probable AMIs among the calls received by the special phone line than calls received by the patients' own doctors, implying that patients did call earlier but were more likely to call their own physician than the special number. The study included a comparison group which was selected by convenience rather than through a randomized design.

A study in Canada employed an eight-week television and radio campaign ("Signals and Actions") to emphasize two concepts: symptoms of a heart attack can be recognized, and it is important to seek immediate professional help (56). A higher percentage of patients presented to the ED within two hours after symptom onset, increasing from 16% to 29% pre-to-post-campaign. Delay time decreased in men during and after the campaign, but increased in women.

A public education media campaign was conducted in Australia three times for one week each, in 1975, 1985, and 1989 (57,58). The percentage of patients admitted to a coronary care unit within four hours of symptom onset increased from 40-50 percent to about 55 percent after the first two media weeks. The effects dwindled after the campaign was discontinued. The third week resulted in no decreases in patient delay.

A six-month community-wide media campaign was conducted in Heidelberg, Germany, which employed mass media, including posters, newspapers, and radioand TV-spots (59). From pre-to-post intervention, hospital admissions within four hours of symptom onset rose from 48 to 81 percent, and median delay time decreased from four hours to 3.2 hours.

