The primary community-level endpoint of REACT is the trend in mean log delay time over the course of the trial. The individual delay times are expected to be sufficiently variable that the trend will be adequately represented by a linear slope β . The null hypothesis of REACT is that on the average β will not differ between the Intervention community and the Control community in each pair.

Delay time will be observed during a four-month baseline period and then over an 18-month intervention period (Figure 6). Each community's trend will be estimated

by simple linear regression, with all baseline observations assigned to time 0. The fitted slope *b* has a standard error asymptotically equal to $\sigma(KV_t)^{-1/2}$, where σ is the residual standard deviation of log delay time; *K* is the total number of cases collected in the community; and V_t is the variance of calendar time at which cases were observed.

The average effect of REACT is estimated by

$$\overline{d} = \sum_{j=1}^{J} \left[b_{j,Intervention} - b_{j,Control} \right] / J$$

where J=10 is the number of community pairs. \overline{d} is an unbiased estimator of the truemean difference between Intervention and Control slopes. Its variance is

$$SE^{2}(\vec{d}) = V(\vec{d}) = 2\sigma_{\beta}^{2}(1-\rho)/J + \sigma^{2}\sum_{j=1}^{J} \left[K_{j,Intervention}^{-1} + K_{j,Control}^{-1}\right]/V_{t}J^{2},$$

where σ_{β}^2 and ρ are respectively the random community-to-community variance and the intra-pair correlation between community-level linear trends.

The primary null hypothesis of the REACT trial is that there is no population ("true") mean difference between Intervention and Control slopes: $H_0:\Delta\beta = \beta\beta_{Intervention} \langle -\beta\beta_{Control} \langle = 0$, where $\langle \rangle$ indicates population expected value. The null hypothesis permits the Control slope to be nonzero and thus allows for secular trend. The alternative hypothesis is that $\Delta\beta\neq 0$; this is a two-sided alternative because it is conceivable (though not likely) that the REACT Intervention could prolong the average delay time.

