The primary hypothesis will be tested with the conventional Type I error rate of α =5% (two-sided). Sample size estimates are based on a paired *t*-test on the values of *d*, or, equivalently, using a mixed-model ANOVA with REACT group as a fixed effect (1 df). Using the *t*-test formulation, the smallest effect detectable with a specified level of power Π is given approximately by

$$\Delta\beta = SE(\overline{d})(t_{\alpha/2} + t_{1-\Pi}),$$

where t_0 demarks the specified upper tail area of the central Student distribution. The degrees of freedom for *t* are *J*-1=9.

The net end-trial effect on delay time is related to slope as follows. After L=1.5 yr of intervention, the difference in mean log delay time between Intervention and Control communities will be $\Delta y = L\Delta\beta$. The corresponding effect on the median delay time will be a multiplicative reduction by a factor of $10^{-L\Delta\beta}$, or

Relative reduction = $100\% \times (1 - 10^{-L\Delta\beta})$, Absolute reduction = $M \times (1 - 10^{-L\Delta\beta})$,

where M is the median delay time at the end of the trial in the Control communities.

C. Results and Sensitivity Analysis

Detectable effects for the primary endpoint in the primary population are shown in Table 5. Three sample sizes are considered: K=800, 600, or 400 complete, usable cases per community. The figure of 600 represents a conservative estimate, based on the above event rates and attrition parameters. For comparison, a "pessimistic" figure of 400 is included, representing the worst-case parameters with an additional 100 cases subtracted for unforeseen attrition. The "optimistic" figure of 800 per community is probably not attainable but has been included as a benchmark for comparison.

In the conservative case (600 per community), which should be easily attained with the broadened eligibility criteria, the detectable absolute reduction is between 27 and 30 min. if the initial median delay is assumed to be 2.5 hr, as much of the available data suggests. If the initial median is taken as 3.0 hr., the absolute level lies between 32 and 35 min.

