The logarithm base 10 of delay times will be used in the analysis to make the distribution less skewed and reduce the impact of a few extreme values. A two stage procedure described by (98) will be adopted. In the first stage, delay times within each community are adjusted for individual level covariates such as the patient's age and gender, and then a community level summary is obtained. The second stage consists of analyzing the community level summaries using analysis of variance. The following linear model will be fit in the first stage:

$$Y_{ijk} = \mu_i + P_{j(i)} + \mathbf{q}^T (\mathbf{x} - \overline{\mathbf{x}}) + \beta_i t + \varepsilon_{ijk}.$$
(1)

The terms in the model are explained below. References will be made to "true" means. This refers to the theoretical mean if an unlimited amount of data could be obtained.

 $Y_{ijk} = \log(\text{delay})$ for the *k*th observation on the *j*th patient in the *i*th community (there may be more than one observation on the same patient).

 μ_i = intercept for the *i*th community. This is the true mean baseline value of log(delay) in the ith community for a patient with average covariate values.

 $P_{j(i)}$ =random patient effect. This is the difference between the true log(delay) for the *j*th patient of the *i*th community and the true mean of all patients in the *i*th community with the same covariate values.

 $\mathbf{x} = \mathbf{x}_{ijk}$ =column vector of individual level covariates for the *k*th observation on the *j*th patient in the *i*th community. These covariates are gender, history of MI, and age.

 $\overline{\mathbf{x}}$ =column vector of average covariate values for all observations in the study.

 \mathbf{q} = column vector of regression coefficients associated with \mathbf{x} .

t=calendar time (time since beginning of study).

 β_i =slope associated with log(delay) versus time in the *i*th community (reflects how rapidly delay times change as the study progresses). A negative value means delay times are decreasing.

 ε_{ijk} = a random error term.

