In this first stage all parameters except $P_{j(i)}$ will be treated as fixed effects, and they will be estimated by maximum likelihood. The $P_{j(i)}$ are random effects. The patients in this study in a given community are regarded as a random sample from all potential MI patients in the community. The above model reduces residual variability by adjusting log(delay) for a limited number of patient specific covariates. The estimates, b_i , of β_i will be used as summary measures in the second stage of the analysis. These are the best estimates of the relationship between log(delay) and calendar time in the *i*th community, adjusted for covariates. For the *k*th community pair, the difference d_k between the intervention and control *b*'s will be computed. A two-tailed, single sample *t*-test of these 10 d_k 's will be performed at α =.05.

The relative improvement in end-of-study delay time for an intervention community compared to a control community with the same intercept will be estimated using a 95% *t*-interval for $\Delta\beta$. Specifically, the confidence interval is

$$\left[10^{2(LL)}, 10^{2(UL)}\right], \tag{2}$$

where *LL* and *UL* are the lower and upper confidence limits for $\Delta\beta$ based on a *t*-interval with nine degrees of freedom.

Analysis will follow the intention-to-treat principle as described in the last section. Every effort will be made to obtain, for each patient, complete information necessary to carry out the primary analysis. It is anticipated that this information will be available on the great majority of patients. For this reason the primary analysis will use the available data only. However, sensitivity analyses will be conducted to determine the effect of missing observations on the results of the study.

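### Formula (2) converts the slope difference to an end-of-study effect with a multiplier of 2, where the protocol's own effect definition and time axis give 1.5

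*Protocol*

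**What the plan says.** Section XI.B.1 defines the effect estimate that accompanies the primary test: "The relative improvement in end-of-study delay time for an intervention community compared to a control community with the same intercept will be estimated". The interval is formula (2), [10^(2·LL), 10^(2·UL)], where LL and UL "are the lower and upper confidence limits for $\Delta\beta$ based on a *t*-interval with nine degrees of freedom". The limits are therefore for the slope difference itself and have not yet been multiplied by any length of time.

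Section X.B, repeated in Appendix C.B, makes the same conversion differently: "After L=1.5 yr of intervention, the difference in mean log delay time between Intervention and Control communities will be" L·Δβ. The median delay is then reduced by a factor of 10^(−L·Δβ).

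The time axis is set out in Section X.B: "Delay time will be observed during a four-month baseline period and then over an 18-month intervention period", and each community's slope is fitted "with all baseline observations assigned to time 0". Appendix C.B bounds the linear decline at 0 ≤ t ≤ 1.5 yr. Section XI.B.5 also sets baseline values to time 0 and says that this follows the primary analysis, but it gives the baseline as six months rather than four. Model (1) in Section XI.B.1, whose slopes feed formula (2), defines t as "calendar time (time since beginning of study". It gives no unit and does not mention setting baseline to 0.

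**The concern.** The protocol defines one quantity, the relative effect at the end of the trial, in two ways that cannot both be right. If two communities share an intercept at t = 0, their ratio of median delay at time t is 10^(t·Δβ). The exponent in formula (2) must therefore equal the value of t at the end of the study. The design sections put that value at 1.5 yr. A multiplier of 2 carries the fitted line half a year past the last observation on that axis.

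Formula (2) is the only conversion of the primary result to the delay-time scale in the analysis section. Section IV.F calls a net reduction of 30-40 min in median delay clinically meaningful, so readers will naturally compare the reported effect with that range and with the detectable reductions in Table 5. Table 5 was computed with 1.5, so an effect computed with 2 is not comparable with it. Sections XI.B.2 to XI.B.4 reuse the primary method for the unadjusted analysis, other delay definitions and other populations, so the multiplier would probably be carried over to them.

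**Working it through.** **Inputs.** From Section X and Appendix C: J = 10 pairs (9 df); baseline B = 0.333 yr; intervention L = 1.5 yr; R = 9; R_β = 1.05 or 1.15; ρ = 0, 0.2 or 0.4; K = 800, 600 or 400 cases per community; 80% power; two-sided 5%. Time is in years because L and V_t are given in years.

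**1. Reproduce the plan's own figure** (K = 600, R_β = 1.05, ρ = 0.4).
- V_t = L³/[3(B+L)] − L⁴/[4(B+L)²] = 0.237 yr², as stated in Appendix C.B.
- σ = ½·log10(9) = 0.477; σ_β = log10(1.05)/(2 × 1.5) = 0.00706.
- SE² = 2σ_β²(1−ρ)/J + σ²(2/K)/(V_t·J) = 0.0000060 + 0.0003201 = 0.0003260, so SE = 0.01806.
- Detectable |Δβ| = 0.01806 × (2.262 + 0.883) = 0.0568 log10 units per year.
- Reduction = 1 − 10^(−1.5 × 0.0568) = 17.8%, which is 26.7 min at M = 2.5 hr and 32.1 min at M = 3 hr. Table 5 prints 18%, 27 and 32.

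With L = 1.5, all 18 rows of Table 5 reproduce to the printed rounding.

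**2. Put the same slope difference through formula (2).** Take an observed Δβ of −0.0568 with 95% limits −0.0568 ± 2.262 × 0.01806, that is −0.0977 to −0.0160.

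| Multiplier | Ratio | 95% interval | Reduction | Minutes at M = 2.5 hr |
|---|---|---|---|---|
| 1.5 (X.B, Appendix C.B) | 0.822 | 0.714 to 0.946 | 17.8% | 26.7 |
| 2 (formula 2) | 0.770 | 0.638 to 0.929 | 23.0% | 34.5 |

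**3. Size in general.** On the log scale the stretch is 2/1.5 = 1.333 for the estimate and for both limits, whatever their sign. On the percent scale, a reduction r is reported as 1 − (1−r)^(4/3): 10% becomes 13.1%, 20% becomes 25.7% and 30% becomes 37.9%. Over the 18 rows of Table 5, the reported reduction is 1.28 to 1.30 times the value at 1.5 yr.

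**4. Other readings of the time axis.**
- *Literal time since the start of the study.* With a four-month baseline, t ends at 22/12 = 1.833 yr. The multiplier 2 is then too large by 2/1.833 = 1.09 on the log scale.
- *Six-month baseline, set to time 0 (Section XI.B.5).* The calendar span is 24 months, but the axis still ends at 1.5 yr, so the stretch is again 1.333.

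**5. Why changing the multiplier alone is not enough.** If t were coded literally and the multiplier changed to 1.5, the effect would be understated: 1.5/1.833 = 0.82 on the log scale. An 18% reduction at 22 months would be reported as 1 − 0.82^(1.5/1.833) = 15.0%. The existing multiplier would give 1 − 0.82^(2/1.833) = 19.5%, which is closer.

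**The case against.** The best defence of the 2 starts from model (1), which feeds formula (2) and describes t as time from the start of the study. Adding the six-month baseline of Section XI.B.5 to 18 months of intervention gives an axis ending at exactly 2 yr. But this needs the six-month figure against the four months in Section X.B and Appendix C.B, and it needs baseline cases left at their calendar dates. The sentence that supplies the six months also puts those cases at time 0 and attributes that coding to the primary analysis. No section supports the combination. What stands is that model (1) is loosely worded and that the size of the error depends on how t is coded. A reader might infer that the multiplier is one third too large however t is coded; the literal reading, with a 9% error, shows that this goes too far.

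Three other stronger inferences are not supported.
- **That the primary conclusion is at risk.** The test is a t-test on ten slope differences and does not use formula (2). Multiplying both limits by a positive constant cannot change whether the interval excludes 1.
- **That a result would be declared clinically meaningful in error.** At M = 2.5 hr, a 23-min effect would indeed appear as 30 min (0.8^0.75 = 0.846, a 15.4% reduction). But formula (2) yields a ratio, Section XI.B.1 does not convert it to minutes, and no decision rule uses it.
- **That the error always flatters the intervention.** A result favouring control would be exaggerated equally.

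The background remark on an Australian media campaign, "The effects dwindled after the campaign was discontinued", gives a reason not to extrapolate past the end of intervention. It concerns one-week campaigns, however, and adds little. The contradiction with L = 1.5 carries the point.

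**Conclusion.** Formula (2) is wrong as written. With baseline cases at 0 and time in years, the reported end-of-study effect and both limits are stretched by one third on the log scale, and reductions of the size in Table 5 are overstated about 1.28 to 1.30 times. The year as the unit is inferred from L and V_t, because model (1) states none. Figures in minutes assume the median delay used in Table 5. Data collection lasts 22 months in all; the 1.5 yr is the length of the slope's axis once baseline is set to 0. The error affects the reported size of the primary effect and its precision on the log scale. It does not affect the test, the p-value or the power. It should be corrected before analysis because it concerns the prespecified primary effect estimate.

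**What to change.** - Replace formula (2) with [10^(1.5·LL), 10^(1.5·UL)], or write L for the multiplier and cite Section X.B.
- State in model (1) that t is in years, with all baseline cases at 0, in line with Section X.B and Appendix C.B. This has to accompany the new multiplier, for the reason in step 5 of the working.
- Reconcile the six-month baseline in Section XI.B.5 with the four months given elsewhere.
- State that the estimate applies at the end of the 18-month intervention and not beyond it.

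The cost is one formula and a few clarifying sentences. No new data are needed, and neither the sample size nor the primary test changes. Reported effects move closer to the null in either direction and become comparable with Table 5.
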